**Self-report Questionnaires.** Negative affect ratings will be assessed at T1 through T5. Perceived stress will be assessed using the Perceived Stress Scale (PSS) at T1 through T5 and both follow-ups. Participants will complete additional self-report questionnaires at T1, T5, and both follow-ups measuring depressive symptoms using the Center for Epidemiologic Studies Scale (CES-D), intensity and nature of grief-related cognitive processes using the Utrecht Grief Rumination Scale (UGRS), and emotion regulation strategy use using the Emotion Regulation Questionnaire (ERQ).

**Functional Magnetic Resonance Imaging.** Participants will complete the picture task at sessions T1 and T5, while undergoing functional magnetic resonance imaging (fMRI) using a simultaneous multislice (SMS)-accelerated (3x) EPI acquisition protocol (63 axial slices; TR=1.2 s; TE=27 ms, 2-mm cubic voxels). Participants will be scanned in a 3.0T Siemens Vida MRI scanner at the Houston Methodist Research Institute outfitted with an MR-compatible LCD display and an MR-compatible 4-response button box. Participants will be screened for metal and other MR-contraindications before entering the scanner.

**RSA.** RSA will be continuously measured during sessions T1 through T5 non-invasively using a Corsense heart rate variability monitor by Elite HRV. RSA will be measured during a 5-minute resting epoch while seated.

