- (1) To determine if a relatively brief, focused intervention in reappraisal-by-distancing in bereaved spouses engages the targeted mechanisms. Hypotheses: Distancing training is expected to result in longitudinal reductions in self-reported negative affect, increases in RSA, and changes in neural activity in a priori ROI's above (i.e., reductions in amygdala activity, increases in DLPFC activity) that are greater than those for reinterpretation training.
- (2) To examine the impact of changes in the targeted mechanisms in changing health-relevant behavior. Hypotheses: Across time and participants, reductions in self-reported negative affect, increases in RSA, and changes in neural activity are expected to lead to reductions in depressive symptoms and grief rumination.
- (3) As an exploratory aim, to mechanistically relate intervention effects to behavior change as a function of changes in the targeted processes. Crucially, this aim will also include assessment of interactions with age and gender of the bereaved spouse and initial depression and grief severity.

Hypotheses: Distancing training will lead to reductions in grief rumination and depression that are mediated by changes in the targeted neurobiological and behavioral mechanisms.

Sample Size::

84 bereaved participants will be recruited (i.e., N=42 per each intervention cell) and randomly assigned to receive either Distancing Training or Reinterpretation Training.

Power Analyses:

Outcome: Self-reported negative affect

Sufficient power to assess self-reported negative affect outcomes will be achieved by recruiting 42 participants per training cell. This sample size estimate is based upon a power analysis using an approximate effect size ($d=.70$) previously reported for within and between-subjects behavioral analyses of longitudinal reappraisal training data¹. Power analyses using this approximate effect size indicate over 95% power ($\alpha=.05$) to detect within-group effects and 90% power ($\alpha=.05$) to detect between-group effects should be achieved with 36 participants per cell. Assuming all-cause attrition of 15% (which reflects a liberal upper bound given past participant attrition rates of approximately 10%), the proposed sample size should provide sufficient power to assess this outcome. Post-attrition, we expect to have analyzable complete data for approximately 36 participants per cell.

Outcome: Respiratory sinus arrhythmia (RSA)

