Data analysis will primarily use linear mixed models, incorporating fixed effects for Training Group (Distancing and Reinterpretation), Session (T1-T5), and Trial Type (for analyses involving the reappraisal task; Look Neutral, Look Negative, and Reappraise Negative), and their interactions, as well as a random effect consisting of an intercept for each participant. In each analysis, statistically significant and near-significant intercept variance reflects reliable differences between participants. We will examine additional models that incorporate and estimate random-effects slope variance across participants on the time effect (i.e., Session). Outcome variables will be repeated measures in self-reported negative affect, RSA⁵, and neural activity (Aim 1) and changes in health-relevant behavioral outcomes (e.g., depressive symptoms and grief rumination; Aims 2 and 3). In these analyses, gender, age, baseline depressive symptoms, expectedness of the loss, and current (non-excluded) medication use will be incorporated as covariates. Importantly, given that we anticipate enrolling an approximately equal number of men and women, we also anticipate having sufficient power to conduct exploratory analyses on the effect of gender (and age) on the hypothesized effects (all Aims). Further, Aim 3 will be investigated using multilevel mediation modeling^{6,7} involving training group assignment as the higher-level predictor (X); self-reported negative affect, RSA data, and neural activity as potential individual-level mediators (M); and health-relevant behavior (i.e., depressive symptoms and grief rumination) as individual-level outcome variables (Y). Note that this will model mediation as a time-dependent and experimental process, both of which help

to rule out alternative explanations. Other exploratory model paths will also be tested. Appropriate covariates indicated above will be incorporated in all mediation models.

Data and Safety Monitoring Plan:

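### The mixed model stated for the Aim 2 outcomes has no mechanism term and its time factor ends at T5, so its coefficients test group and session differences in symptoms, not whether mechanism change leads to symptom change.

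*SAP*

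**What the plan says.** **The hypothesis.** SAP, Specific Aims, states Aim 2 as "To examine the impact of changes in the targeted mechanisms in changing health-relevant behavior". Its hypothesis names three classes of mechanism (self-reported negative affect, RSA, neural activity) and ends: "changes in neural activity are expected to lead to reductions in depressive symptoms and grief rumination". Aim 3 is labelled exploratory. Aim 2 is not.

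**The model.** SAP, Data Analysis, All Outcomes, gives one mixed-model specification, "incorporating fixed effects for Training Group (Distancing and Reinterpretation), Session (T1-T5), and Trial Type". Trial type applies only to analyses of the reappraisal task. The model adds interactions, "as well as a random effect consisting of an intercept for each participant", and random session slopes in additional models. The covariates are gender, age, baseline depressive symptoms, expectedness of the loss and medication use.

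**Roles of the variables.** The mechanisms are outcomes: "Outcome variables will be repeated measures in self-reported negative affect, RSA⁵, and neural activity (Aim 1". Symptom measures are the outcomes for the other two aims: "changes in health-relevant behavioral outcomes (e.g., depressive symptoms and grief rumination; Aims 2 and 3". The same section then describes a multilevel mediation model for Aim 3, with training group as predictor, the mechanisms as mediators, and depressive symptoms and grief rumination as outcomes. It also mentions further exploratory paths without naming variables, times or an aim.

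**The schedule.** Protocol, Self-report Questionnaires, on CES-D and UGRS: "Participants will complete additional self-report questionnaires at T1, T5, and both follow-ups". Protocol, Design, puts the follow-ups at one and two months after the intervention and the fMRI scans at T1 and T5. Negative affect and RSA are measured at every session from T1 to T5.

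**The concern.** Aim 2 concerns an association between two things measured on the same person: how far a mechanism moved, and how far symptoms moved. Such a question needs the mechanism on the right-hand side of the model. The specification attached to the Aim 2 outcomes has none, so it answers a different question: do symptoms differ by training group and session?

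Two things are at stake. First, a group or session effect on CES-D could be reported as support for Aim 2 when it says nothing about mechanism, and a true association could go unseen because the two groups improved equally. Second, if the mechanism term is added once data are in hand, its form is still open: level or change, concurrent or lagged, one mechanism at a time or jointly, and which task contrast. That freedom can produce an association by selection.

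The time factor is a separate, lesser weakness. It stops at T5, so the two later symptom assessments, which would help give the phrase about leading to reductions a time order, have no stated place in the analysis.

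**Working it through.** **1. The plan's own figures.** SAP, Power Analyses, gives d = .70, α = .05 and 36 per cell, with over 95% power within group and 90% between groups.
- Between groups, noncentral t: .903 one-sided, .834 two-sided. The 90% is reproduced only if α is one-sided; the SAP does not state sidedness.
- Within group, two-sided: .983, which agrees.
- Attrition: 42 × 0.85 = 35.7, about 36 per cell and 72 in all.

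None of these figures concerns a mechanism-to-symptom association. The SAP gives no effect size or power for one.

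**2. Aim 2 against the stated model.**

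| Element | Aim 2 needs | Stated mixed model has |
|---|---|---|
| Outcome | Depressive symptoms, grief rumination | The same |
| Predictor | Change in negative affect, RSA, neural activity | Group, session, group × session |
| Adjustment | Group and covariates | Five covariates, none a mechanism |
| Time | Mechanism change, then symptom change | T1-T5 only |

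The predictor row settles the point. No coefficient in the right-hand column is a mechanism effect.

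**3. Does it matter in practice?** A simulation of T1-T5 change scores used 36 per cell, 4,000 replicates, two-sided .05, standard normal mechanism change m, and symptom change y = c·group + b·m + √(1 − b²)·e. The values of b and c are assumptions.

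| True state | Group-only test rejects | Mechanism term rejects |
|---|---|---|
| b = 0.3, no group effects | 5.0% | 73% |
| b = 0.4, no group effects | 5.0% | 94% |
| b = 0.5, no group effects | 4.6% | 99.6% |
| b = 0, direct group effect c = 0.7 SD | about 84% | about 4-5% |

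The group term can miss a real association entirely and can be significant when there is none.

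**4. The time factor.** CES-D and UGRS have four planned times: T1, T5, one month and two months. Two of the four fall within T1-T5. If the outcome is change from T1, only one value per person remains by T5, and a participant intercept then cannot be separated from residual error. Neural change and symptom change also span the same T1-to-T5 interval, so within that window they have no time order.

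**5. What a proper Aim 2 test could detect.** Fisher z: r = tanh[(z for α + z for power)/√(N − 3 − k)], with N = 72, two-sided α and 80% power (z = 0.842). Here k is the number of other person-level terms.
- Unadjusted, k = 0: tanh[(1.960 + 0.842)/√69] = .325, about .33.
- With k = 6 (group, T1 outcome and four other covariates at one degree of freedom each): tanh[2.802/√63] = .339, about .34.
- Eight tests (negative affect, RSA, amygdala, DLPFC × two outcomes), Bonferroni .05/8: tanh[(2.734 + 0.842)/√69] = .406, about .41.
- Six tests, if neural activity counts as one mechanism, .05/6: tanh[(2.638 + 0.842)/√69] = .396, about .40.

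With no correction, and if eight tests were independent, the chance of at least one false positive would be 1 − .95⁸ = 34%.

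**The case against.** The strongest reply is that the All Outcomes text is a shared template for what the analysis will primarily use, not a closed equation for Aim 2. It cannot be literal for every outcome, since fMRI exists only at T1 and T5. The mediation model does contain a path from each mechanism to symptoms, adjusted for group and covariates, and that path estimates something close to the Aim 2 association.

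Much of this stands, and it rules out three stronger readings.
- A reader might infer that the SAP contains no estimate at all of a mechanism-to-symptom link. It does contain one, in the Aim 3 mediation model. What remains is that the SAP assigns this model to Aim 3 only, labels that aim exploratory, and leaves the additional paths undefined.
- A reader might infer that the follow-up symptom data are excluded. The SAP is silent on them: its time factor does not cover them, but no text rules them out.
- A reader might infer that the follow-ups are the only symptom data after mechanism change. That does not hold for negative affect and RSA, which are measured at each session, so T1-T4 change precedes the T5 questionnaires. It does hold for fMRI, which is not repeated between T1 and T5.

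The template argument does not rescue the plan. A template that names the Aim 2 outcomes and lists its predictors is what an analyst would follow, and nothing else in the SAP is assigned to Aim 2.

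**Conclusion.** The concern holds for the model the SAP states for the Aim 2 outcomes, not for the SAP as a whole. That model's coefficients do not test the Aim 2 hypothesis, and the only mechanism-to-symptom path belongs to an exploratory aim. This is more than missing detail: followed as written, the model answers a different question. The omission of the one- and two-month assessments from the time factor is a secondary weakness, because the missing mechanism term alone defeats the test.

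The conclusion rests on the content of the model and on no numerical assumption. The simulation slopes are illustrative. The detectable correlations assume 72 evaluable participants, two-sided α and one change score per person. The count of eight tests takes amygdala and DLPFC separately, as in Aim 1; Aim 2 itself says only neural activity. The point should be corrected before the Aim 2 analysis is run.

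**What to change.** State a separate mixed model for Aim 2.
- **Outcome:** CES-D, and in a second set of models UGRS, at T5 and both follow-ups.
- **Predictor of interest:** T1-to-T5 change in one mechanism per model. Define negative affect and neural activity each by one prespecified task contrast.
- **Other terms:** training group, time, the T1 value of the outcome, the other listed covariates and a participant random intercept. In the CES-D model the T1 value takes the place of the baseline depressive symptoms covariate, so that it is not entered twice.
- **Test:** the coefficient of mechanism change, with a stated multiplicity rule across mechanisms and the two outcomes.
- **Sensitivity analysis:** follow-up symptoms adjusted for T5 symptoms. The main model still contains symptom change that occurred between T1 and T5, and this analysis supports the time ordering.

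The cost is SAP wording, code and more analysis work. All the data needed are in the planned schedule; the documents do not say how much has been collected. The price of honest multiplicity control is a less favourable detectable association, about .41 rather than about .33 under Bonferroni over eight tests. The SAP should say so, or name a smaller primary set of associations.

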### **Design:**

Recently-bereaved participants (i.e. approximately 6 months post-spousal loss) will be screened for eligibility, then randomly assigned to receive training in either distancing or reinterpretation, with five sessions occurring every 1-3 days, with longitudinal collection of affective, psychophysiological, and functional magnetic resonance imaging (fMRI) data. During the five sessions (T1-T5), participants will undergo cognitive emotion regulation training and an emotion regulation task in their respective training groups, complete questionnaires, and take a 5 minute RSA reading. Functional MRI scans will be acquired at T1 and T5. Follow-up questionnaire assessments of perceived stress, depressive symptoms and grief rumination will occur at one and two months post-intervention. We propose to recruit 84 participants in this study (i.e., 42 participants per intervention cell).

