Statistical Analysis Plan

Study Title: Neural Mechanisms of Enhancing Emotion Regulation in Bereaved Spouses

ClinicalTrial.gov Identifier: NCT04822194

Sponsor: The National Institute on Aging

Intervention: Cognitive Emotion Regulation Training

Protocol Number: 1

Phase: Phase 1

Statistical Analysis Plan Version: 1.0

May 21, 2025

Principal Investigator: [name]

Rice University

[name]

[name]

United States of America

Statistical Analysis Plan

Introduction:

The objective of this research study is to examine the efficacy and behavioral and neural mechanisms of a cognitive emotion regulation training intervention in bereaved spouses. The primary endpoints are the assessments of the psychological, psychophysiological, and neural mechanisms mediating behavior change as a function of the cognitive emotion regulation intervention. Psychological mechanisms will be assessed by emotion regulation task-based self-reported negative affect. Psychophysiological mechanisms will be investigated by analysis of respiratory sinus arrhythmia data, a measure of heart rate variability reflecting adaptive cardiac vagal tone. Neural mechanisms will be assessed via analysis of fMRI data. The secondary endpoint is testing the efficacy of the intervention via assessment of psychological outcomes (i.e., the behavior change, as represented in changes in depressive symptoms, stress, and grief rumination).

Objectives:

This study represents a Phase I, Stage I clinical trial. The project builds upon promising preliminary work to investigate the effectiveness and underlying neurobiological mechanisms of a novel, five-session cognitive reappraisal intervention in bereaved spouses. The study aims to mechanistically relate changes in psychological, psychophysiological, and neural function during a novel emotion regulation intervention never before implemented in this stressed, high risk group. The goal is to inform future interventions that can reduce negative psychological outcomes in bereaved spouses.

Specific Aims:

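### Grief rumination and perceived stress are compared between arms as change from T1; adjusting for each outcome's own T1 score, with T1 taken out of the responses, is usually more precise at almost no cost

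*SAP*

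**What the plan says.** The SAP Introduction makes efficacy the secondary endpoint, "as represented in changes in depressive symptoms, stress, and grief rumination". The SAP's Power Analyses section claims between-group power for the questionnaire outcomes, so an arm comparison is intended.

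Under Data Analysis, All Outcomes, the SAP fits linear mixed models with "fixed effects for Training Group (Distancing and Reinterpretation), Session (T1-T5") and their interactions, plus a random intercept. T1 is therefore a level of Session. The same section names as responses for the later aims "changes in health-relevant behavioral outcomes (e.g., depressive symptoms and grief rumination; Aims 2 and 3"). Its covariate sentence reads: "In these analyses, gender, age, baseline depressive symptoms, expectedness of the loss, and current (non-excluded) medication use will be incorporated as covariates". Nothing removes T1 from the responses or sets the arms equal at T1.

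On timing, the Protocol (Methods, Self-report Questionnaires) collects PSS "at T1 through T5 and both follow-ups". For CES-D, UGRS and ERQ it says: "Participants will complete additional self-report questionnaires at T1, T5, and both follow-ups". The Protocol's Design section describes a course "with five sessions occurring every 1-3 days" and adds: "Follow-up questionnaire assessments of perceived stress, depressive symptoms and grief rumination will occur at one and two months post-intervention".

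**The concern.** Whether the response is a change score or the repeated scores including T1, the arm comparison for UGRS and PSS is a difference in change from T1. In the second case it is the Group x Session interaction. The one baseline score in the covariate list is an own baseline for CES-D but not for UGRS or PSS.

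T1 is not ignored, and the contrast is unbiased under randomisation. What is at stake is efficiency. Subtracting T1 gives it a weight of exactly 1. When T1 and the later score are imperfectly correlated and have similar spread, the best weight is smaller, so change over-corrects for chance differences between the arms at T1. Those T1 scores are already scheduled, so the precision is there to be used.

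The point concerns the arm comparisons only. It does not bear on the Aim 2 association.

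**Working it through.** **The plan's own figure.** For questionnaire outcomes the SAP uses d = .70, alpha .05 and 36 per cell, and states 90% between-group power. With noncentrality .70 × √(36/2) = 2.970 on 70 df, the t-test has power .903 one-sided and .834 two-sided. The 90% is thus reproduced only one-sided, and sidedness is not stated. Attrition is consistent: 42 × .85 = 35.7, about 36. Two-sided tests are used below.

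**Assumed input.** The documents give no correlation rho between T1 and a later score, so .3 to .9 is shown. T5 falls 4 to 12 days after T1 (four gaps of 1 to 3 days), so the upper values are more plausible there. The lower ones are more relevant to the one- and two-month scores.

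**Variance per participant, T1 SD = 1, later SD = k.**
- Change from T1: 1 + k² − 2·rho·k
- Own-T1 adjustment: k²(1 − rho²), times 1 + 1/68 for estimating the slope
- 95% CI half-width: t × √(2 × variance/36), with 70 df for change and 69 df for adjustment

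At k = 1 the ratio is (1 − rho²)/[2(1 − rho)] = (1 + rho)/2:

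| rho | Change | Own T1 | Ratio | Net variance cut | Half-width, T1 SDs | Power, d = .70 in raw SD | Power, d = .70 in change SD |
|---|---|---|---|---|---|---|---|
| .3 | 1.400 | 0.910 | .65 | 34.0% | 0.556 to 0.452 | .697 to .862 | .834 to .950 |
| .5 | 1.000 | 0.750 | .75 | 23.9% | 0.470 to 0.410 | .834 to .919 | .834 to .919 |
| .7 | 0.600 | 0.510 | .85 | 13.8% | 0.364 to 0.338 | .966 to .983 | .834 to .884 |
| .8 | 0.400 | 0.360 | .90 | 8.7% | 0.297 to 0.284 | .996 to .998 | .834 to .865 |
| .9 | 0.200 | 0.190 | .95 | 3.6% | 0.210 to 0.206 | above .99 both | .834 to .847 |

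Break-even after the slope cost is at rho of about .97.

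**Where the loss comes from.** At k = 1, 2(1 − rho) = (1 − rho²) + (1 − rho)². The excess is the chance T1 difference, with standard error √(2/36) = .236 SD, passed through at weight 1 − rho: .165/.118/.071/.047/.024 SD. This is the same loss seen from another side, not an additional one.

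**Unequal SDs.** The entry minimum of 25 on a grief inventory could narrow the spread at T1. At k = 1.2 (assumed), the change variances are 1.720/1.240/0.760/0.520/0.280 and the adjusted ones 1.310/1.080/0.734/0.518/0.274. The net cut is 22.7/11.6/1.9/−1.2/0.8%.

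**Does baseline CES-D already do the work?** With T1 among the responses, a CES-D main effect leaves Group x Session unchanged in balanced data. With a change-score response it acts as a proxy. If CES-D correlates c with own T1, and T5 relates to CES-D only through own T1, the change variance becomes 2(1 − rho) − ((1 − rho)c)². Before the slope cost, own-T1 adjustment still cuts variance by 32.9/23.3/13.8/9.2/4.6% at c = .3 and 21.5/14.5/8.3/5.4/2.6% at c = .7.

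**PSS over five sessions.** With a common correlation of .5/.7/.8, constraining the arms to be equal at T1 gives variance ratios of .75/.85/.90 with categorical Session and .75/.86/.91 with linear Session.

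**The obvious but wrong remedy.** In 100,000 simulated null trials (k = 1, T1 and T5 as responses, T1 also a covariate, random intercept, REML, 70 df), the Group x Session estimate kept its empirical SD of .280/.236/.183/.150/.105. The model SE fell to .253/.220/.175/.145/.104, and type I error was 7.4/6.5/5.9/5.6/5.4%. Own-T1 adjustment on the same data had a type I error of 5.0 to 5.1% and empirical variance cuts of 33.9/23.7/13.9/8.5/3.6%.

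**The case against.** The strongest objection is size. Where rho is high, as is likely at T5, half-widths move only from 0.36 to 0.34 or less, and with unequal SDs the gain can vanish. That stands. But the worst loss in the grid is 1.2% of variance against a possible gain of about a third, and lower correlations are more plausible at the follow-ups. It is also true that Session is defined as T1 to T5, so no follow-up contrast is written. That is a reason to write one, not to leave the role of T1 open.

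No sentence sets out the UGRS or PSS arm contrast, and Aim 1's comparison with reinterpretation covers other outcomes. The contrast is inferred, but the secondary endpoint and the between-group power claim both imply it. Exploratory Aim 3 brings in initial grief severity, but only as a moderator and with no instrument named.

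A mixed model with T1 as a response can also use participants seen only at T1. With 36 completers and 6 T1-only participants per arm (assumed pattern, equal SDs, covariance treated as known), the planned contrast has variance (1 − rho²)/36 + (1 − rho)²/42 per arm. The net cut then falls from 34/24/14/9/4% to 31/21/12/7/3%. This is real but small.

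Finally, an unstructured covariance over seven PSS visits has 7 × 8/2 = 28 parameters, to be estimated from about 72 participants. That is a fair caution about the constrained-baseline route; the covariate route does not depend on it.

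**Conclusion.** The concern holds, as a point of efficiency and not of bias. On either reading of the SAP, UGRS and PSS are compared between arms as change from T1, with no own-baseline adjustment. At 36 per cell and equal SDs, own-T1 adjustment lowers the variance of the contrast by 34% at rho .3, 14% at .7 and 4% at .9, net of its cost. The size rests on rho and on the ratio of SDs, neither of which the documents give; at an SD ratio of 1.2 the gain is nil from about rho .7. Because two-sided power for d = .70 is about .83 and not the stated 90%, even a moderate gain is worth having if d is read on the change-score scale. Both methods need T1 scores taken before training, which the Protocol's Design section does not establish: it places training and questionnaires in the same session without giving their order.

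**What to change.** For the arm comparison of each questionnaire outcome, state the response, the visits and the role of T1. Use one of two forms:

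- **(a)** Model the post-T1 scores (T5, one and two months; for PSS also T2 to T4), with that outcome's own T1 score and its interaction with visit as covariates, and T1 removed from the responses.
- **(b)** Keep T1 as a response in a constrained-baseline model with a common T1 mean for both arms and an unstructured covariance over visits, without that outcome's T1 as a covariate.

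Do not add T1 as a covariate while it stays a response. Apply the same rule to CES-D, where the listed baseline covariate would create exactly that situation if T1 CES-D is also a response. T1 CES-D can remain a covariate for UGRS and PSS.

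Confirm in the SAP that T1 questionnaires are completed before T1 training. If they are not, T1 is not a true baseline, neither form applies, and the planned change contrast is affected too.

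Form (a) costs SAP wording and about one degree of freedom per post-T1 visit modelled. Form (b) adds covariance parameters, which matters most for PSS. No new data are needed. Record the change before the arm comparisons are run.

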Sufficient power to assess questionnaire outcomes (i.e., depressive symptoms, grief rumination, perceived stress, and reappraisal usage frequency) will be achieved by recruiting 42 participants per training cell. This sample size estimate is based upon a power analysis using an approximate effect size ($d=.70$) previously reported for within and between-subjects analyses of questionnaire reports measuring these variables (e.g., depressive symptoms²; perceived stress¹). Power analyses using this approximate effect size indicate over 95% power ($\alpha=.05$) to detect within-group effects and 90% power ($\alpha=0.05$) to detect between-group effects should be achieved with 36 participants per cell. Assuming all-cause attrition of 15% (which reflects a liberal upper bound given past participant attrition rates of approximately 10%), the proposed sample size should provide sufficient power to assess this outcome. Post-attrition, we expect to have analyzable complete data for approximately 36 participants per cell.

Definitions of Populations to be Analyzed:

Conditions or Focus of Study

- Bereavement
- Emotions
- Emotion Regulation
- Psychophysiology
- Social Affective Neuroscience

Eligibility Criteria

Inclusion Criteria:

- Recent bereavement of loved one (i.e. loss of romantic partner within the past 5-7 months)
- At least 18 years of age, with no maximum age, provided all other inclusion and exclusion criteria are met.
- Minimum score of 25 on the Inventory for Complicated Grief

- Must be able to speak, read, and write in English
- Must be eligible to safely complete MRI scanning

Exclusion Criteria:

- Death of a second close family member/friend in the past year
- If they are currently receiving psychotherapy
- If they have obstructive pulmonary and/or heart disease, diabetes, liver failure, or kidney failure
- If they have a significant visual, auditory, or cognitive impairment that compromises their ability to understand and complete the task
- If they've gotten divorced within the past year
- Prior participation in similar emotion regulation training protocol in [name] lab
- If they have any contraindication to MRI scanning (i.e. pregnancy, presence of any non-removable metal on or in the body, implanted medical devices, tattoos, medication patches, orthodontic braces or permanent retainers, hearing aids, and history of claustrophobia or breathing disorders)

Data Analysis:

All Outcomes

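### Baseline depressive symptoms is a covariate in the depressive-symptom model as well, where T1 CES-D appears also to be a response, so the between-arm contrast gains no baseline adjustment

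*SAP*

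**What the plan says.** The Data Analysis section of the SAP, under All Outcomes, sets out one model: "Data analysis will primarily use linear mixed models, incorporating fixed effects for Training Group (Distancing and Reinterpretation), Session (T1-T5), and Trial Type", with their interactions, "as well as a random effect consisting of an intercept for each participant". Random slopes on Session come only in additional models. The outcomes for Aims 2 and 3 are "changes in health-relevant behavioral outcomes (e.g., depressive symptoms and grief rumination; Aims 2 and 3"). The covariate sentence follows directly: "In these analyses, gender, age, baseline depressive symptoms, expectedness of the loss, and current (non-excluded) medication use will be incorporated as covariates". It makes no exception for the depressive-symptom model, and it names neither the instrument nor the visit that supplies the baseline.

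The protocol (Methods, Self-report Questionnaires) gives the schedule: "Participants will complete additional self-report questionnaires at T1, T5, and both follow-ups measuring depressive symptoms" with the CES-D. No other depression measure appears in either document. The SAP Introduction makes efficacy the secondary endpoint, described as "the behavior change, as represented in changes in depressive symptoms, stress, and grief rumination". For questionnaire outcomes the power section claims "90% power ($\alpha=0.05$) to detect between-group effects should be achieved with 36 participants per cell", at d = 0.70.

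**The concern.** For negative affect, RSA, neural activity and grief rumination, baseline depressive symptoms is an ordinary covariate. For depressive symptoms it is, by inference, the outcome's own first value. A model with a Session factor starting at T1 and a participant intercept needs T1 as a response row, so the same score then stands on both sides of the equation.

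Two things are at stake. A covariate that is constant within a person cannot adjust a within-person contrast, so the plan appears to adjust for baseline but forgoes the precision that this should bring. Also, with only two response rows, the covariate removes so much between-person variance that the random intercept is estimated as zero and the error term becomes too small. The SAP's reading of intercept variance as evidence of differences between participants would then fail for this outcome.

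**Working it through.** **Inputs.** From the SAP: 36 analyzable per arm, alpha 0.05, d = 0.70. From the protocol: CES-D at T1, T5 and two follow-ups, so only T1 and T5 fall within Session T1-T5. Assumed, because the documents give no figure: T1-T5 correlation r from 0.3 to 0.8, equal variances (SD 1), complete data, and a true difference of 0.5 SD as an illustration alongside the plan's 0.70.

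**The plan's own figure.** With d = 0.70 and 36 per arm, the noncentrality is 0.70/√(2/36) = 2.97. Power is 83.4% two-sided and 90.3% one-sided (t test), so the stated 90% is reproduced only one-sided; the SAP does not state sidedness. Within-group power is 98.3% two-sided, consistent with the claim of over 95%. The calculations below are two-sided.

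**Step 1: the contrast is not adjusted.** With complete data, Group x Session is estimated from within-person differences, and a main-effect T1 covariate cancels out of these. Fits to single simulated datasets confirm it. With two rows the estimate is 0.0213 with the covariate, and the raw difference in change is 0.0213. With four rows both are -0.2190.

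**Step 2: what that costs.** The per-person variance is 2(1-r) for raw change and 1-r² with T1 as covariate only. The noncentrality is 0.5/√(variance x 2/36). At r = 0.5 this is 0.5/√(1.00/18) = 2.12 for change and 0.5/√(0.75/18) = 2.45 for the covariate analysis.

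| r | Variance, change | Variance, T1 as covariate | Power, change | Power, T1 as covariate |
|---|---|---|---|---|
| 0.3 | 1.40 | 0.91 | 42% | 59% |
| 0.5 | 1.00 | 0.75 | 55% | 67% |
| 0.7 | 0.60 | 0.51 | 77% | 82% |
| 0.8 | 0.40 | 0.36 | 91% | 93% |

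The last column allows for estimating the slope on T1; the plain formula gives up to about one point more. At the plan's d = 0.70, simulated power for change against T1 as covariate is 70% against 87% (r = 0.3), 83% against 93% (r = 0.5) and 96% against 98% (r = 0.7).

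**Step 3: test size with two rows (T1 and T5).** The within-person mean square is 1-r. The between-person mean square given T1 is (1-r²)/2 = (1-r)(1+r)/2, which is always smaller in expectation. An intercept variance bounded at zero is therefore estimated as zero, and the error is pooled to about (1-r)(3+r)/4. The ratio of true to modelled variance is 4/(3+r).

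| r | 4/(3+r) | Size, formula | Size, simulated | Intercept variance at zero |
|---|---|---|---|---|
| 0.3 | 1.212 | 7.5% | 7.6% | 100% |
| 0.5 | 1.143 | 6.7% | 7.0% | 100% |
| 0.7 | 1.081 | 5.9% | 6.2% | 99% |
| 0.8 | 1.053 | 5.6% | 5.6% | 96% |

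There were 12,000 simulated trials per correlation. Without the covariate, the size was 4.9% to 5.3%.

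**Step 4: other readings.** With four rows (T1, T5 and both follow-ups) under compound symmetry, the intercept variance is zero in 2.7% of trials at r = 0.3 and in at most 0.01% at r = 0.5 or more. The size is 4.7% to 5.2%. With a T5-T1 change score as outcome and T1 as covariate, the size is 4.6% to 5.4% and the baseline adjustment is genuine.

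**The case against.** The strongest objection is that the double use of T1 is inferred. The SAP contrasts repeated measures for Aim 1 with changes in outcomes for Aims 2 and 3, and the Introduction also defines the secondary endpoint as change. If that means a change score, T1 is not a response row and the covariate is ordinary ANCOVA. This stands as a possible reading, but it sits badly with the stated model. A single T5-T1 change per person leaves no Session factor and no separately estimable intercept.

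A reader might infer that the between-arm CES-D test runs above 5% in any case and that the intercept variance is zero by construction. The documents do not support that. Both effects need the two-row layout, and even there the variance is almost always, not always, zero. The protocol collects CES-D at four visits. With all four modelled under compound symmetry, the covariate adds no inflation. Under an AR(1) correlation the four-row size is 6.0% to 7.2%, but it is identical with and without the covariate, so the covariate is not the cause.

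The size of the effect also depends on the correlation. Sessions are 1 to 3 days apart, so T1 and T5 are about 4 to 12 days apart (four intervals). A high correlation is then plausible, and both the excess size and the lost power are smaller there.

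Finally, the outcome is secondary. Aim 2 is an association across participants and Aim 3 is exploratory mediation. The between-arm CES-D contrast follows from the efficacy wording and from the power section, which claims between-group power for depressive symptoms. This limits the weight of the point but does not remove it.

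**Conclusion.** The point holds in a limited form. The SAP gives the depressive-symptom model its own baseline as a covariate while the stated model terms imply that T1 is also a response. On either repeated-outcome reading (two rows or four), with complete data, the Group x Session contrast gets no baseline adjustment. The forgone power at 0.5 SD and 36 per arm is about 17 percentage points at r = 0.3 (59 - 42), 12 at 0.5, 5 at 0.7 and 2 at 0.8. The excess size of roughly 0.5 to 2.5 points belongs to the two-row reading only. On a change-score reading there is nothing to correct beyond saying so.

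These figures assume that the covariate is T1 CES-D, that variances are equal and that r lies between 0.3 and 0.8. The point concerns one secondary outcome; the covariate can stay as it is for the others.

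**What to change.** For the depressive-symptom outcome only, state that T1 CES-D is a covariate and not a response. Model the post-T1 scores (T5, and the follow-ups if they are included) on Group, visit, Group x visit, T1 CES-D and T1 CES-D x visit, and test the group difference at a named visit. If T5 is the only post-T1 visit modelled, the visit terms drop out and this is ANCOVA. If a change score was intended, say so and keep T1 as covariate.

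Keeping T1 as a response and dropping the covariate is a fallback. It restores the correct size in the two-row case but gives only the raw-change precision, so it is not equivalent.

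The cost is a few lines of SAP text and one changed model statement, with no new data. Participants who have only a T1 CES-D would leave this model.
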